Survival information (e.g., date and cause of death, post-treatment cancer therapies, including transplantation) will be collected once the subject's disease has progressed via telephone calls (e.g., to subject or family member) and/or clinical visits at 12 weeks intervals (± 1 week) after the subject's last study visit for a period of 1 year after last subject's last dose or possibly sooner if all patients have discontinued and most patients have expired.

Section 5.4.1 Discontinuation of Individual Subjects

Subsection COVID-19 Pandemic-Related Acceptable Protocol Modification

Add: new subsection title and text

COVID-19 Pandemic-Related Acceptable Protocol Modification

During the COVID 19 pandemic, it has been necessary to employ mitigation strategies to enable the investigator to ensure subject safety and continuity of care. Refer to the Section 5.3.1.1, Study Procedures and Table 3 for details on how to handle study activities/procedures accordingly. Study drug interruptions due to COVID-19 restrictions should be captured in EDC.

The investigator should contact the sponsor medical contact before discontinuing a subject from the study for a reason other than "planned per protocol," to ensure all acceptable mitigation steps have been explored.

Section 5.4.2 Discontinuation of Entire Study

Subsection Interruption/Discontinuation of Study Drug Due to COVID-19 Infection

Add: new subsection title and text

Interruption/Discontinuation of Study Drug Due to COVID-19 Infection

Decisions to delay or interrupt any study treatment based on the current situation and any concern for active infection should be made by the treating investigator after considering the subject's current oncologic status and treatment tolerance, as well as their general medical condition. As a potentially serious infection, consideration for treatment interruption is advised. If needed, any questions can be discussed with the Therapeutic Area Medical Director (TAMD).

Section 5.5.1 Treatments Administered

Subsection COVID-19 Pandemic-Related Acceptable Protocol Modifications

Add: new subsection title and text

COVID-19 Pandemic-Related Acceptable Protocol Modifications

If a subject is unable to come to the study site to pick up their study drug due to COVID-19, a direct-to-patient (DTP) venetoclax shipment can be made from the study site to the subject if allowed by local regulations. Cytarabine DTP are is not allowed by AbbVie. AbbVie will submit any required notifications to the regulatory authority as applicable.

Venetoclax may be shipped from the study site directly to the study subject's home if all the following criteria are met:

- Direct-to-patient (DTP) shipment of venetoclax is allowed by local regulations and the relevant ethics committee
- Venetoclax can be administered by the subject (or subject's caregiver) at home

- Subject agrees to have the venetoclax shipped directly to their home
 - Shipments may also include other study supplies (e.g., drug dosing diaries). Instructions will be provided by AbbVie as to how a study site can initiate a DTP shipment using Marken, a global vendor selected by AbbVie to provide this service when necessary. Shipments of venetoclax from the study site to a subject's home will be appropriately temperature controlled (qualified shipper or temperature monitoring) within the labeled storage conditions. Signature is required upon delivery; due to COVID-19 related social distancing, this may be provided by the courier after delivery. Documentation of the shipment is to be retained by the clinical site.
 - AbbVie will not receive subject identifying information related to these shipments, as the site will work directly with the courier.

The study site is responsible for meeting IRB/IEC reporting requirements related to DTP shipments of study drug, and for obtaining consent to provide delivery information to the courier and documenting this consent in source documents.

Section 6.1.6 Adverse Event Reporting

Subsection COVID-19 Pandemic-Related Acceptable Protocol Modifications

Add: new subsection title and text

COVID-19 Pandemic-Related Acceptable Protocol Modifications

Supplemental study case report forms should be completed in the event of COVID-19 related missed/virtual visits, study drug interruptions or discontinuations, or adverse events (including capture of specific signs/symptoms of infection and testing results).

COVID-19 infections should be captured as adverse events. If the event meets the criteria for a serious adverse event (SAE), then follow the SAE reporting directions per the protocol and above. The following COVID-19 related supplemental eCRFs should be completed (for both serious and non-serious events):

- COVID -19 Supplemental Signs/ Symptoms
- COVID-19 Status Form

Section 7.0 Protocol Deviations

First paragraph, last sentence previously read:

If a protocol deviation occurs (or is identified) after a subject has been enrolled, the principal investigator is responsible for notifying Independent Ethics Committee (IEC)/Independent Review Board (IRB) regulatory authorities (as applicable), and the following AbbVie Clinical Monitor(s):

Has been changed to read:

If a protocol deviation occurs (or is identified, including those that may be due to COVID-19 pandemic) after a subject has been enrolled, the principal investigator is responsible for notifying Independent Ethics Committee (IEC)/Independent Review Board (IRB) regulatory authorities (as applicable), and the following AbbVie Clinical Monitor(s):

Section 9.2 Ethical Conduct of the Study

Last sentence previously read:

Responsibilities of the clinical investigator are specified in Appendix A.

Has been changed to read:

In the event a significant disaster/crisis (e.g., epidemic/pandemic, natural disaster, conflict/combat) occurs leading to difficulties in performing protocol-specified procedures, AbbVie may engage with study site personnel in efforts to ensure the safety of subjects, maintain protocol compliance, and minimize risks to the integrity of the study while trying to best manage subject continuity of care. This may include alternative methods for assessments (e.g., phone contacts or virtual site visits), alternative locations for data collection (e.g., use of a local lab instead of a central lab), and shipping investigational product and/or supplies direct to subjects to ensure continuity of treatment where allowed. In all cases, these alternative measures must be allowed by local regulations and permitted by IRB/IEC. Investigators should notify AbbVie if any urgent safety measures are taken to protect the subjects against any immediate hazard.

Responsibilities of the clinical investigator are specified in [Appendix A](#).

Section 9.3 Subject Information and Consent

Add: new last paragraph

Due to the COVID-19 pandemic, it is possible that additional protocol modifications not outlined in this protocol may become necessary. If this situation arises, in addition to the study informed consent, additional verbal consent may be obtained prior to these adaptations or substantial changes in study conduct in accordance with local regulations.

Section 10.2 Case Report Forms

Add: new fourth paragraph

During the COVID-19 pandemic, remote monitoring of data may be employed if allowed by the local regulatory authority, IRB/IEC, and the study site.

2.1 Summary of Versions

Version	Date of Completion	Summary
1.0	19 Dec 2017	First version (Appendix of Briefing Book of FDA Type C Meeting)
2.0	04 May 2018	Implemented comments from FDA
3.0	27 Nov 2018	Update the version date for 2 nd interim CSR
4.0	02 Oct 2019	Update the version date for 3 rd interim CSR

2.2 List of Abbreviations and Definitions of Terms

AE	Adverse event
AESI	Adverse Event of Special Interest
AML	Acute Myeloid leukemia
AST	Aspartate aminotransferase
HMA	Azacitidine or Decitabine
LDAC	Low dose cytarabine
MedDRA	Medical dictionary for regulatory activities
MPN	Myeloproliferative neoplasm
NCI	National Cancer Institute
NCI CTC	National Cancer Institute Common Terminology Criteria
PT	Preferred term
RBC	Red blood cell
SAE	Serious adverse event
SAP	Statistical analysis plan
SMQ	Standardized MedDRA query
SOC	System organ class
TEAE	Treatment-emergent adverse event
ULN	Upper limit of normal
WBC	White blood cells
WHO	World Health Organization

3.0 Introduction

This efficacy SAP covers the statistical procedure for the efficacy analyses of the data from Studies M14-358 (R&D/17/1341) and M14-387 (R&D/17/1340). These analyses will support the efficacy assessment of venetoclax for AML. Analyses will be performed by personnel from Data and Statistical Sciences at AbbVie or their designees using SAS Version 9.3 or later (SAS Institute Inc., Cary, NC 27513) under the UNIX operating system.

4.0 Objectives for Statistical Analysis Plan

This SAP provides the details of the statistical analyses planned to be performed for the efficacy assessment of Studies M14-358 and M14-387. The analyses will include all AML subjects who had at least one dose of venetoclax.

5.0 Studies/Protocols

A complete list of relevant clinical studies associated with venetoclax that will be contributed to the product efficacy assessment is listed in [Table 1](#).

Table 1. Studies to be Included in Efficacy Summary

Study ID Phase (Status)	Number of Enrolled Subjects (Actual/Planned)	Location	Study Design	Primary Objective
M14-358 Phase 1b (Enrollment complete and follow-up is ongoing)	212/260	Australia, Germany, France, and US	Open-label study of venetoclax + azacitidine or decitabine in treatment naïve elderly (≥ 60 years) subjects with AML who are not eligible for standard induction therapy; 2 stages: dose escalation and dose expansion (both HMAs)	Evaluate the safety, PK, and efficacy of venetoclax + decitabine or azacitidine in the target population. The objective of the safety expansion is to confirm efficacy and safety of the intended dose for Phase 3 study.
M14-387 Phase 1/2 (Enrollment complete and follow-up is ongoing)	92/92	Australia, Germany, Italy, US	Open-label study of venetoclax + LDAC in treatment naïve subjects with AML who are ≥ 60 years of age and who are not eligible for standard anthracycline-based induction therapy; 2 stages: dose escalation and safety expansion	Phase 1: Evaluate the safety, PK and determine the MTD and RPTD of venetoclax + LDAC. Phase 2: Estimate efficacy, including ORR, and characterize the toxicity of the combination at the RPTD. Cohort C: Evaluate the ORR for subjects allowed additional supportive medications (strong CYP3A inhibitors) if medically indicated.

The venetoclax doses and regimens in the Studies listed in [Table 1](#) are described in [Table 2](#) below.

Table 2. Regimens Investigated in Venetoclax AML Studies

Study ID	Venetoclax Dose and Frequency	Treatment Regimen
M14-358	Venetoclax 400 mg QD, 800 mg QD, 1200 mg QD	Venetoclax in combination with HMA (Azacitidine or Decitabine)
M14-387	Venetoclax 600 mg QD, 800 mg QD	Venetoclax in combination with LDAC (Low dose cytarabine)

6.0 Analysis Sets

6.1 Definition of Analysis Sets and Rationale

This efficacy SAP provides details of statistical analyses that are to be performed for the efficacy assessment of Studies M14-358 and M14-387. The analyses for Studies M14-358 and M14-387 will not be pooled and three analysis sets will be prepared for summaries of efficacy as detailed in [Table 3](#). The reason for not pooling the Studies M14-358 and M14-387 is that the different treatment regimens (venetoclax monotherapy, venetoclax in combination with azacitidine, venetoclax in combination with decitabine, and venetoclax in combination with LDAC) are expected to have different efficacy profiles. Thus, it is not appropriate to pool data across these studies to assess the efficacy of venetoclax.

Table 3. Definition of the Analysis Sets

Analysis Data Sets	Studies Included	Study Population	Treatment Groups
1. Venetoclax in combination with HMA	M14-358	Subjects who received at least one dose of venetoclax	
 • venetoclax 400 mg QD + azacitidine (N = 84) • venetoclax 800 mg QD + azacitidine (N = 37) • overall of venetoclax + azacitidine (N = 127) • venetoclax 400 mg QD + decitabine (N = 31) • venetoclax 800 mg QD + decitabine (N = 37) • overall of venetoclax + decitabine (N = 73) • DDI venetoclax 400 mg QD (N = 12)
2. Venetoclax in combination with LDAC	M14-387	Subjects who received at least one dose of venetoclax	
 • venetoclax 600 mg QD + LDAC (N = 82) • venetoclax 600 mg QD + LDAC without MPN (N = 78) • All Subjects (venetoclax 600 mg QD + LDAC or Venetoclax 800 mg QD + LDAC) (N = 92)

1) Venetoclax in combination with HMA Analysis Set

This analysis set includes subjects who received at least one dose of venetoclax in Study M14-358. This analysis dataset will be used to provide a comprehensive summary of efficacy of venetoclax in combination with HMA (azacitidine 75 mg/m² daily administered intravenously or subcutaneously [Days 1 - 7] or decitabine 20 mg/m² daily administered intravenously [Days 1 - 5] during each 28 day cycle).

2) Venetoclax in combination with LDAC Analysis Set

This analysis set includes subjects who received at least one dose of venetoclax in Study M14-387.

This analysis dataset will be used to provide a comprehensive summary of efficacy of venetoclax in combination with LDAC (20 mg/m² daily administered subcutaneously [Days 1 - 10]). Patients with an antecedent history of myeloproliferative neoplasm (MPN) including polycythemia vera, myelofibrosis, essential thrombocythemia, or chronic myelogenous leukemia were excluded from the study in Study M14-387 Protocol

Amendment 2 because emerging evidence suggested that patients with JAK2 mutated MPN may not benefit from treatment with venetoclax in combination with LDAC. To explore the efficacy of venetoclax in combination with LDAC both including and excluding those patients with a history of MPN will be presented.

Unless otherwise stated, data included in efficacy analyses is subjected to the cutoff date which is determined at each interim analysis.

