4.0 Study Objective

The primary objectives of the Phase 1 portion are to assess the safety profile, characterize PK, determine the dose schedule, the maximum tolerated dose (MTD), and the recommended Phase 2 dose (RPTD) of venetoclax (ABT-199/GDC-0199) in combination with LDC in treatment-naïve subjects with AML who are ≥ 65 years of age and who are not eligible for standard induction therapy due to co-morbidity or other factors.

The primary objectives of the initial Phase 2 portion of the study are to evaluate the preliminary estimates of efficacy including the overall response rate (ORR), and to characterize the toxicities of the combination at the RPTD.

The primary objective of Phase 2 Cohort C is to evaluate the ORR for subjects allowed additional supportive medications (strong CYP3A inhibitors) if medically indicated.

The secondary objectives of the initial Phase 2 portion and Phase 2 Cohort C are to evaluate leukemia response (rates of CR, CRi, PR, and MLFS), duration of response (DOR) and overall survival (OS).

Additional exploratory objectives of both phases of the study may be evaluated to find biomarkers that may serve as surrogates or predictors for clinical outcomes in future studies of venetoclax in AML.

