8.0 Statistical Methods and Determination of Sample Size

8.1 Statistical and Analysis Plans

Analysis will be performed separately for each phase of the study.

Efficacy and safety analyses will be performed on all subjects who receive at least one dose of venetoclax.

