6.2 Planned Efficacy Analyses for Each Analysis Dataset

A list of contents of efficacy analyses described in the Statistical Methods section (Section 8.0) is provided below. The list of analyses will be performed for all three analysis datasets separately. Data will not be pooled across studies.

- Complete remission (CR) rate (Analysis datasets 1 - 3)
- Complete remission with partial hematologic recovery (CRh) rate (Analysis datasets 1 - 3)
- CR + CRh rate (Analysis datasets 1 - 3)
- CR + CRh rate by the initiation of Cycle 2 (Analysis datasets 1 - 3)
- Time to the first response of CR + CRh (Analysis datasets 1 - 3)
- Time to best response of CR + CRh (Analysis datasets 1 - 3)
- Duration of CR (Analysis datasets 2 - 3)
- Duration of CR + CRh (Analysis datasets 1 - 3)
- CR + CRi rate (Analysis datasets 2 - 3)
- CR + CRi rate by the initiation of Cycle 2 (Analysis datasets 2 - 3)
- Time to the first response of CR + CRi (Analysis datasets 2 - 3)
- Time to best response of CR + CRi (Analysis datasets 2 - 3)
- Duration of CRi (Analysis datasets 2 - 3)
- Duration of CR + CRi (Analysis datasets 2 - 3)
- Objective Response Rate (CR + CRi + PR) (Analysis datasets 2 - 3)
- Overall survival (OS) (Analysis datasets 2 - 3)

- Post baseline RBC/Platelet transfusion independence and duration of post baseline RBC/Platelet transfusion independence (Analysis datasets 1 - 3)
- Time to first RBC/platelet transfusion (Analysis datasets 2 - 3)
- Time to the first recurrent RBC/platelet transfusion (Analysis dataset 2 - 3)
- Time to first Grade 3 or above TEAE hemorrhage event (SMQ narrow) (Analysis datasets 2 - 3)
- Time to first Grade 3 or above TEAE SOC of "infections and infestations" event (Analysis datasets 2 - 3)
- Time to first hospitalization due to SAE (Analysis datasets 2 - 3)

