8.1 Efficacy Analyses

Unless otherwise specified, all summaries/analyses of efficacy data will be presented for all treatment groups of the analysis datasets 1 – 3 specified in [Table 3](#) separately. There will be no pooled analyses across the three analysis datasets. All subjects who have received at least one dose of venetoclax will be included in the efficacy analyses. Unless otherwise stated, the data cutoff date will be applied to efficacy analyses for Study M14-358 and Study M14-387 (Analysis dataset 2 - 3).

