8.1.13 Subgroup Assessment of Efficacy Variables

The subgroup analyses will be performed for Studies M14-358 and M14-387 including the following treatment groups.

Study M14-358:

1. overall of venetoclax + azacitidine (N = 127)
2. venetoclax 400 mg + azacitidine (N = 84)
3. overall of venetoclax + decitabine (N = 73)

Study M14-387:

1. venetoclax 600 mg QD + LDAC or venetoclax 800 mg QD + LDAC (N = 92)
2. venetoclax 600 mg QD + LDAC (N = 82)
3. venetoclax 600 mg QD + LDAC and without MPN (N = 78).

No subgroup analyses will be performed for Study M14-212 due to relative small number of patients in this study.

CR rate, CR + CRh rate, post-baseline transfusion independence rate, duration of CR, duration of CR + CRh, and OS will be assessed for the subgroups within each treatment group as defined below.

- Gender (Male, Female)
- Age (< 75 years, ≥ 75 years)
- By modified Ferrara Criteria (Y, N)
- By Cytogenetics (Intermediate risk, poor risk)
- Type of AML (primary, secondary)
- AML MDS related changes (Yes, No)
- Prior HMA use (Yes, No) (only for Study M14-387)
- Biomarker mutation (TP53, FLT3, IDR1/2, NPM1)
- Moderate/Strong CYP3A inhibitors (Y, N)

In addition, number of percentage of CR/CRh subjects went on post-treatment therapy will be summarized.

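### No M14-387 group in the efficacy SAP isolates the initial Phase 2 portion or Cohort C, so neither primary ORR has a planned output

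*SAP*

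**What the plan says.** **Protocol.** Section 4.0 names ORR as a primary objective of the initial Phase 2 portion, and for the later cohort it says "The primary objective of Phase 2 Cohort C is to evaluate the ORR". Section 5.1 describes three portions: Phase 1, initial Phase 2 and Cohort C. Section 8.1 states "Analysis will be performed separately for each phase of the study". Section 8.1.3.1.1 defines ORR as CR, CRi or PR and asks for a binomial 95% interval. Section 8.2 tabulates Clopper-Pearson intervals separately for 50 subjects (Table 13) and 20 subjects (Table 14). Sections 5.6.1 and 8.2 say that Cohort C is there to show whether its ORR departs from, or agrees with, that of subjects treated earlier.

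**Efficacy SAP.** Table 1 in Section 5.0 repeats the objective: "Cohort C: Evaluate the ORR for subjects allowed additional supportive medications (strong CYP3A inhibitors) if medically indicated". Section 6.2 lists "Objective Response Rate (CR + CRi + PR) (Analysis datasets 2 - 3". Section 8.1 sets the default that "all summaries/analyses of efficacy data will be presented for all treatment groups of the analysis datasets", referring to Table 3. For M14-387, Table 3 has 600 mg (N = 82), 600 mg without MPN (N = 78) and "All Subjects (venetoclax 600 mg QD + LDAC or Venetoclax 800 mg QD + LDAC) (N = 92". Section 9.0 adds that the full analysis set combines escalation and expansion. In the subgroup section (8.1.13), "CR rate, CR + CRh rate, post-baseline transfusion independence rate, duration of CR, duration of CR + CRh, and OS will be assessed". ORR is absent from that list, and no factor there is study portion or cohort.

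**The concern.** The protocol asks for ORR by portion. The SAP groups the study by dose and MPN history instead. Its own table of objectives and its own table of groups therefore do not match, and Protocol Tables 13 and 14 have no corresponding SAP output.

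The portions differ in ways that could affect response. Protocol 8.2 lists, for Cohort C, more objective entry criteria with a lower age limit, dose modification for strong CYP3A inhibitors, and allowance for reduced liver or kidney function. The ramp-up schedule also differs. A pooled ORR is a weighted average over these portions and does not estimate Cohort C's rate. Since no hypothesis test is planned, the estimate and its interval are the whole primary result for each portion.

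**Working it through.** **1. Match the SAP groups to the protocol portions.**

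| SAP group | N | Portions it contains |
|---|---|---|
| 600 mg | 82 | Phase 1 at 600 mg, initial Phase 2, Cohort C |
| 600 mg without MPN | 78 | the same, less 82 − 78 = 4 subjects |
| All subjects | 92 | the same as the first row, plus 92 − 82 = 10 subjects at 800 mg |

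The 600 mg level is both the Phase 1 starting level and the Phase 2 dose, so the 600 mg groups must include Phase 1 subjects. The planned Phase 2 total, 50 + 20 = 70, equals none of 82, 78 or 92.

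**2. Check whether the subgroups supply the split.** The nearest factor is use of moderate or strong CYP3A inhibitors (yes/no). It is defined by use rather than by cohort, it includes moderate inhibitors, and ORR is not among its endpoints.

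**3. Reproduce the protocol's intervals.** For x responders of n, the Clopper-Pearson limits are the 2.5% quantile of Beta(x, n−x+1) and the 97.5% quantile of Beta(x+1, n−x).

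| x/n | Computed 95% interval | Protocol |
|---|---|---|
| 30/50 | 45.2 to 73.6% | 45, 74 |
| 25/50 | 35.5 to 64.5% | 35, 64 |
| 20/50 | 26.4 to 54.8% | 26, 55 |
| 15/50 | 17.9 to 44.6% | 18, 45 |
| 14/20 | 45.7 to 88.1% | 46, 88 |
| 12/20 | 36.1 to 80.9% | 36, 81 |
| 10/20 | 27.2 to 72.8% | 27, 73 |
| 8/20 | 19.1 to 63.9% | 19, 64 |

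All eight agree within 1 point. The largest distance from estimate to limit is 14.8 points at n = 50, so the stated 15-point margin holds, and 24.3 points at n = 20 (ORR 40% to 70%).

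**4. Margin in the pooled group.** For n = 82: 33/82 gives 29.6 to 51.7%, 41/82 gives 38.7 to 61.3%, and 49/82 gives 48.3 to 70.4%. The largest margin is 11.4 points.

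**5. Share of each portion in the N = 82 group.** The documents do not give the split. Assuming the targets were met at 600 mg, Cohort C is 20/82 = 24.4% and initial Phase 2 is 50/82 = 61.0%. If Cohort C held 15 to 25 subjects, its share is 15/82 = 18.3% to 25/82 = 30.5%.

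**6. What pooling could hide (illustration).** Take 20 Cohort C subjects and 82 − 20 = 62 others, with 37/62 (60%) of the others responding.

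- If Cohort C has 6/20 = 30% (95% interval 12 to 54%), the pooled result is 43/82 = 52% (41 to 64%).
- If Cohort C has 8/20 = 40% (19 to 64%), the pooled result is 45/82 = 55% (44 to 66%).

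Halving the Cohort C rate relative to the others would move the reported figure by less than 8 points.

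**7. Precision of a descriptive difference.** The half-width is 1.96·√[p(1−p)(1/20 + 1/n₂)], with p from 0.4 to 0.6.

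| Comparator | n₂ | Half-width (points) |
|---|---|---|
| All earlier subjects, 92 − 20 | 72 | 24.3 to 24.8 |
| Earlier subjects at 600 mg, 82 − 20 | 62 | 24.7 to 25.2 |
| Initial Phase 2 alone | 50 | 25.4 to 25.9 |

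**The case against.** The strongest reply is that the protocol still governs. It fixes the endpoint, the non-responder rule and the interval, and the SAP nowhere says it replaces them. This is also a two-study document, re-dated for the second and third interim study reports, and a separate final plan may exist. This much stands: the by-portion requirement has not been withdrawn. But the SAP does serve study reports, no other efficacy plan is among the documents, and anyone programming from it would not produce either primary ORR.

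Second, the by-phase rule in Protocol 8.1 may mean only Phase 1 against Phase 2. That is a fair reading, but the SAP fails it too, because its groups combine both. The further split rests on the separate objectives in Section 4.0 and the separate tables in Section 8.2.

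Third, the default in SAP 8.1 allows for exceptions. None is specified for ORR.

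Fourth, Cohort C is small, and an interval on the difference would settle little. The half-widths above bear out the second part, so the difference should be descriptive. Smallness is no reason to omit the cohort: the protocol tabulated n = 20 in advance, and SAP Table 3 carries "DDI venetoclax 400 mg QD (N = 12" for M14-358. That comparison is only suggestive. Those 12 subjects lie outside both combination totals (127 + 73 + 12 = 212) and would otherwise not appear, and the documents do not describe their design.

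Finally, the SAP's emphasis on CR and CR + CRh may reflect regulatory comments noted in its version log. That can justify extra endpoints, but it does not remove the protocol's primary one.

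**Conclusion.** The concern holds. Followed as written, the efficacy SAP yields three pooled ORR estimates for M14-387 and neither of the two that the protocol names as primary. No printed figure is wrong; the gap is in the reporting groups. It must be fixed, because two primary objectives have no planned output.

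The conclusion needs no assumption about numbers, since it follows from the group definitions. Its size does depend on the unstated split. With 50 and 20 subjects at 600 mg, Cohort C makes up about a quarter of the N = 82 group (18% to 30% for 15 to 25 subjects), and a margin of about 11 points replaces margins of up to 24 and 15 points. The masking example also assumes a 60% ORR in the other 62 subjects.

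**What to change.** - Add two M14-387 groups to efficacy SAP Table 3: initial Phase 2 at the recommended Phase 2 dose, and Phase 2 Cohort C.
- Report ORR (CR + CRi + PR) with a Clopper-Pearson 95% interval in each, labelled as the primary efficacy output of that portion. SAP 8.1 has no ORR subsection, so add one carrying the protocol's definition and non-responder rule. Correct the dataset numbering at the same time: Section 6.2 assigns ORR to datasets 2 and 3, but Table 3 defines only 1 and 2.
- Report the ORR difference between Cohort C and earlier subjects with a 95% interval, descriptively and without a test. Use the Phases 1 and 2 comparator from Protocol 5.6.1, with initial Phase 2 alone as an option. State that the half-width is about 24 to 26 points.
- Keep the N = 82, 78 and 92 groups as supportive summaries.

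The cost is SAP wording and one extra table on data already collected. The drawback is wider intervals than the pooled one (largest margins 24 and 15 points against 11), which the protocol's own tables already accept.
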